10.3.6. Data Quality Assurance

Data Quality Assurance/Quality Control

Steps to be taken to ensure the accuracy and reliability of data include the selection of qualified investigators and appropriate study sites, review of protocol procedures with the investigator and study site personnel before the study periodic monitoring visits by the sponsor, and direct transmission of clinical laboratory data from a central laboratory into the sponsor's data base. Written instructions will be provided for collection, handling, storage, and shipment of samples.

Guidelines for CRF completion will be provided and reviewed with study site personnel before the start of the study.

The sponsor will review CRF for accuracy and completeness during on-site monitoring visits and after transmission to the sponsor; any discrepancies will be resolved with the investigator or designee, as appropriate. After upload of the data into the study database they will be verified for accuracy and consistency with the data sources.

10.3.7. Case Report Form Completion

Case report forms are prepared and provided by the sponsor for each participant in electronic format. All data relating to the study must be recorded in CRF. All CRF entries, corrections, and

alterations must be made by the investigator or authorized study site personnel. The investigator must verify that all data entries in the CRF are accurate and correct.

The study data will be transcribed by study site personnel from the source documents onto an electronic CRF, if applicable. Study-specific data will be transmitted in a secure manner to the sponsor.

Worksheets may be used for the capture of some data to facilitate completion of the CRF. Any such worksheets will become part of the participant's source documents. Data must be entered into CRF in English. The CRF must be completed as soon as possible after a participant visit and the forms should be available for review at the next scheduled monitoring visit.

If necessary, queries will be generated in the electronic data capture (eDC) tool. If corrections to a CRF are needed after the initial entry into the CRF, this can be done in either of the following ways:

- Investigator and study site personnel can make corrections in the eDC tool at their own initiative or as a response to an auto query (generated by the eDC tool).
- Sponsor or sponsor delegate can generate a query for resolution by the investigator and study site personnel.

10.3.8. Source Documents

At a minimum, source documents consistent in the type and level of detail with that commonly recorded at the study site as a basis for standard medical care must be available for the following: participant identification, eligibility, and study identification; study discussion and date of signed informed consent; dates of visits; results of safety and efficacy parameters as required by the protocol; record of all AEs and follow-up of AEs; concomitant medication; intervention receipt/dispensing/return records; study intervention administration information; and date of study completion and reason for early discontinuation of study intervention or withdrawal from the study, if applicable.

The author of an entry in the source documents should be identifiable.

Specific details required as source data for the study and source data collection methods will be reviewed with the investigator before the study and will be described in the monitoring guidelines (or other equivalent document).

The minimum source documentation requirements for Section 5.1, Inclusion Criteria and Section 5.2, Exclusion Criteria that specify a need for documented medical history are as follows:

- Referral letter from treating physician or
- Complete history of medical notes at the site
- Discharge summaries

Inclusion and exclusion criteria not requiring documented medical history must be verified at a minimum by participant interview or other protocol-required assessment (eg, physical examination, laboratory assessment) and documented in the source documents.

An eSource system may be utilized, which contains data traditionally maintained in a hospital or clinic record to document medical care (eg, electronic source documents) as well as the clinical study-specific data fields as determined by the protocol. This data is electronically extracted for use by the sponsor. If eSource is utilized, references made to the eCRF in the protocol include the eSource system but information collected through eSource may not be limited to that found in the eCRF.

10.3.9. Monitoring

The sponsor will use a combination of monitoring techniques central, remote, or on-site monitoring to monitor this study.

The sponsor will perform on-site monitoring visits as frequently as necessary. The monitor will record dates of the visits in a study site visit log that will be kept at the study site. The first post-initiation visit will be made as soon as possible after enrollment has begun. At these visits, the monitor will compare the data entered into the eCRF with the source documents (eg, hospital/clinic/physician's office medical records). The nature and location of all source documents will be identified to ensure that all sources of original data required to complete the CRF are known to the sponsor and study site personnel and are accessible for verification by the sponsor study site contact. If electronic records are maintained at the study site, the method of verification must be discussed with the study site personnel.

Direct access to source documents (medical records) must be allowed for the purpose of verifying that the recorded data are consistent with the original source data. Findings from this review will be discussed with the study site personnel. The sponsor expects that, during monitoring visits, the relevant study site personnel will be available, the source documents will be accessible, and a suitable environment will be provided for review of study-related documents. The monitor will meet with the investigator on a regular basis during the study to provide feedback on the study conduct.

In addition to on-site monitoring visits, remote contacts can occur. It is expected that during these remote contacts, study site personnel will be available to provide an update on the progress of the study at the site.

Central monitoring will take place for data identified by the sponsor as requiring central review.

10.3.10. On-Site Audits

Representatives of the sponsor's clinical quality assurance department may visit the study site at any time during or after completion of the study to conduct an audit of the study in compliance with regulatory guidelines and company policy. These audits will require access to all study records, including source documents, for inspection. Participant privacy must, however, be

respected. The investigator and study site personnel are responsible for being present and available for consultation during routinely scheduled study site audit visits conducted by the sponsor or its designees.

Similar auditing procedures may also be conducted by agents of any regulatory body, either as part of a national GCP compliance program or to review the results of this study in support of a regulatory submission. The investigator should immediately notify the sponsor if he or she has been contacted by a regulatory agency concerning an upcoming inspection.

10.3.11. Record Retention

In compliance with the ICH/GCP guidelines, the investigator/institution will maintain all CRF and all source documents that support the data collected from each participant, as well as all study documents as specified in ICH/GCP Section 8, Essential Documents for the Conduct of a Clinical Trial, and all study documents as specified by the applicable regulatory requirement(s). The investigator/institution will take measures to prevent accidental or premature destruction of these documents.

Essential documents must be retained until at least 2 years after the last approval of a marketing application in an ICH region and until there are no pending or contemplated marketing applications in an ICH region or until at least 2 years have elapsed since the formal discontinuation of clinical development of the investigational product. These documents will be retained for a longer period if required by the applicable regulatory requirements or by an agreement with the sponsor. It is the responsibility of the sponsor to inform the investigator/institution as to when these documents no longer need to be retained.

If the responsible investigator retires, relocates, or for other reasons withdraws from the responsibility of keeping the study records, custody must be transferred to a person who will accept the responsibility. The sponsor must be notified in writing of the name and address of the new custodian. Under no circumstance shall the investigator relocate or dispose of any study documents before having obtained written approval from the sponsor.

If it becomes necessary for the sponsor or the appropriate regulatory authority to review any documentation relating to this study, the investigator/institution must permit access to such reports.

10.3.12. Study and Site Start and Closure

First Act of Recruitment

The first site open is considered the first act of recruitment and it becomes the study start date.

Study/Site Termination

The sponsor reserves the right to close the study site or terminate the study at any time for any reason at the sole discretion of the sponsor. Study sites will be closed upon study completion. A study site is considered closed when all required documents and study supplies have been collected and a study site closure visit has been performed.

The investigator may initiate study site closure at any time, provided there is reasonable cause and sufficient notice is given in advance of the intended termination.

Reasons for the early closure of a study site by the sponsor or investigator may include but are not limited to:

- Failure of the investigator to comply with the protocol, the requirements of the IEC/IRB or local health authorities, the sponsor's procedures, or GCP guidelines
- Inadequate recruitment of participants by the investigator
- Discontinuation of further study intervention development

10.4. Appendix 4: Adverse Events, Serious Adverse Events, Product Quality Complaints, and Other Safety Reporting: Definitions and Procedures for Recording, Evaluating, Follow-up, and Reporting

10.4.1. Adverse Event Definitions and Classifications

Adverse Event

An AE is any untoward medical occurrence in a clinical study participant administered a pharmaceutical (investigational or non-investigational) product. An AE does not necessarily have a causal relationship with the intervention. An AE can therefore be any unfavorable and unintended sign (including an abnormal finding), symptom, or disease temporally associated with the use of a medicinal (investigational or non-investigational) product, whether or not related to that medicinal (investigational or non-investigational) product. (Definition per ICH)

This includes any occurrence that is new in onset or aggravated in severity or frequency from the baseline condition, or abnormal results of diagnostic procedures, including laboratory test abnormalities.

Note: The sponsor collects AEs starting with the signing of the ICF (refer to All Adverse Events under Section 8.3.1, Time Period and Frequency for Collecting Adverse Event and Serious Adverse Event Information, for time of last AE recording).

Serious Adverse Event

A SAE based on ICH and EU Guidelines on Pharmacovigilance for Medicinal Products for Human Use is any untoward medical occurrence that at any dose:

- Results in death
- Is life-threatening (The participant was at risk of death at the time of the event. It does not refer to an event that hypothetically might have caused death if it were more severe.)
- Requires inpatient hospitalization or prolongation of existing hospitalization
- Results in persistent or significant disability/incapacity
- Is a congenital anomaly/birth defect
- Is a suspected transmission of any infectious agent via a medicinal product
- Is Medically Important*

*Medical and scientific judgment should be exercised in deciding whether expedited reporting is also appropriate in other situations, such as important medical events that may not be immediately life-threatening or result in death or hospitalization but may jeopardize the participant or may require intervention to prevent one of the other outcomes listed in the definition above. These should usually be considered serious.

If a serious and unexpected AE occurs for which there is evidence suggesting a causal relationship between the study intervention and the event (eg, death from anaphylaxis), the event must be reported as a serious and unexpected suspected adverse reaction even if it is a component of the study endpoint (eg, all-cause mortality).

Unlisted (Unexpected) Adverse Event/Reference Safety Information

An AE is considered unlisted if the nature or severity is not consistent with the applicable product reference safety information. For guselkumab, the expectedness of an AE will be determined by whether or not it is listed in the IB.

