9.4.5. Safety Analyses

All safety analyses will be made on the Safety Population.

Adverse Events

The verbatim terms used in the eCRF by investigators to identify AEs will be coded using the Medical Dictionary for Regulatory Activities (MedDRA). Treatment-emergent AEs are AEs with onset during the treatment phase or that are a consequence of a preexisting condition that has worsened since baseline.

Adverse events, SAEs, related AEs, and AEs by severity will be summarized by treatment group. More specification of other AESIs such as ILD will be described in the SAP.

Summaries, listings, or participant narratives may be provided, as appropriate, for those participants who die, who discontinue intervention due to an AE, or who experience a severe or an SAE.

Clinical Laboratory Tests

The laboratory parameters and change from baseline in selected laboratory parameters (hematology and chemistry), and the number of participants with abnormal laboratory parameters (hematology and chemistry) based on National Cancer Institute Common-Terminology Criteria for Adverse Events (NCI-CTCAE) toxicity grading will be summarized by intervention group.

Electrocardiogram

Clinically relevant abnormalities will be evaluated by frequency tabulations.

Vital Signs

Descriptive statistics of temperature, pulse/heart rate, respiratory rate, and blood pressure (systolic and diastolic) values and changes from baseline will be summarized at each scheduled time point. The percentage of participants with values beyond clinically important limits will be summarized.

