5.7.2. Adverse Events

The verbatim terms used in the CRF by investigators to identify adverse events will be coded using the Medical Dictionary for Regulatory Activities (MedDRA). Any AE occurring at or after the initial administration of study intervention is considered to be treatment emergent. If the event occurs on the day of the initial administration of study intervention, and either event time or time of administration are missing, then the event will be assumed to be treatment emergent. If the event date is recorded as partial or completely missing, then the event will be considered to be treatment emergent unless it is known to be prior to the first administration of study intervention based on partial onset date or resolution date. All reported treatment-emergent adverse events will be included in the analysis. For each adverse event, the number and percentage of participants who experience at least 1 occurrence of the given event will be summarized by intervention group.

Summary tables will be provided for treatment-emergent adverse events in the main study period and LTE period:

- AEs
- Serious AEs (SAEs)
- AEs leading to discontinuation of study intervention
- AEs by severity
- AEs by relationship to study intervention
- AEs leading to drug interruption

- Infusion reaction
- Injection site reaction
- Covid-19 related AEs and SAEs

In addition to the summary tables, listings will be provided for participants who:

- Had SAEs
- Had AEs leading to discontinuation of study intervention

Incidence of other treatment-emergent adverse events of special interest will be summarized. See [Appendix 8](#) for list of adverse events in each category.

Deaths will be displayed by actual intervention received. Frequencies for the following parameters will be included in the summary table:

- Number of participants who died
- Cause of death
- Relationship to study intervention (yes/no)

A listing of participants who died will be provided.

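### SAP 5.7.2 drops the protocol's worsening route to treatment-emergent status without declaring it, so a screening-onset AE that worsens on study intervention can go uncounted, depending on how the worsening is recorded

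*Protocol*

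**What the plan says.** Protocol 9.4.5 gives two routes to treatment-emergent status: "Treatment-emergent AEs are AEs with onset during the treatment phase or that are a consequence of a preexisting condition that has worsened since baseline". SAP 5.7.2 gives one, based on timing: "Any AE occurring at or after the initial administration of study intervention is considered to be treatment emergent". Where the event date is partial or missing, the SAP defaults to counting the event, "unless it is known to be prior to the first administration of study intervention based on partial onset date or resolution date". SAP Appendix 2, which is the place to record departures from the protocol's planned analyses, is marked not applicable.

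Two statements in Protocol 10.4.1 bear on which records exist. On what counts as an AE: "This includes any occurrence that is new in onset or aggravated in severity or frequency from the baseline condition". On when collection starts: "The sponsor collects AEs starting with the signing of the ICF". Screening may last up to 6 weeks (Protocol 1.3, Table 1).

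On scope, SAP 5.7.2 states: "Summary tables will be provided for treatment-emergent adverse events in the main study period and LTE period". For events of special interest: "Incidence of other treatment-emergent adverse events of special interest will be summarized". The secondary safety endpoint (Protocol section 3, SAP Table 1) is the number and proportion of participants with treatment-emergent AEs, SAEs or AESIs.

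**The concern.** The SAP should implement the protocol's definition in more technical detail. Here it narrows the definition and does not say so. The part removed concerns a preexisting problem that gets worse after dosing starts, which is one way that a drug effect can show itself. Because AEs are recorded from consent, an event may already be in the database with a pre-dose start date when the first dose is given. If it later becomes severe, serious or a reason for stopping, the protocol treats it as treatment-emergent. Under the SAP, its status may depend on how the site entered the worsening. A secondary safety endpoint should not turn on an unstated data-entry habit.

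**Working it through.** No figure in the plan can be reproduced here. The check sets the two rules against the possible histories of an event.

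1. **New event, onset after first dose.** Treatment-emergent under Protocol 9.4.5 (first route) and under SAP 5.7.2. The documents agree.
2. **Event present before first dose and unchanged afterwards.** Not treatment-emergent under either. The documents agree.
3. **Event present before first dose, worsens after dosing, worsening entered as a new AE with its own post-dose date.** Treatment-emergent under both. Protocol 10.4.1 supports this entry, because it makes an aggravation from the baseline condition an AE in its own right.
4. **Same history, but the worsening is entered as a change of severity on the original record, which keeps its pre-dose start date.** Treatment-emergent under Protocol 9.4.5 (second route). Not treatment-emergent under SAP 5.7.2 if an AE is taken to occur at its onset.

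Only case 4 separates the documents, and it needs two conditions.

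- *Occurrence means onset.* The SAP does not say so outright. Its rule for incomplete dates judges timing from the onset or resolution date, which points that way, but that rule covers incomplete dates only.
- *The worsening sits on the old record.* Protocol 10.4.5 (AE procedures) and 10.3.7 (CRF completion) do not say whether a worsening AE gets a new record. Protocol section 8 lists eCRF completion instructions among the site materials. Those are not in the documents reviewed.

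In case 4 the event is missing from the treatment-emergent AE and AESI summary tables in SAP 5.7.2, and so from the endpoint built on them.

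On size, the planned arm is 28 participants, so one participant is 1/28 = 0.0357, or 3.6 percentage points. That shift arises only if the participant has no other qualifying event in the period, because the summary counts participants with at least one occurrence. The documents give no rate of screening-onset AEs, no rate of worsening and no recording convention, so an expected number cannot be calculated.

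**The case against.** The strongest reply is that the two documents can be read together without any loss. An aggravation is an AE under Protocol 10.4.1, and an aggravation after dosing is an AE occurring after dosing, so the SAP already counts it. Protocol 10.4.1 refers to the baseline condition and draws no line between conditions that predate consent and events that began in screening. This stands as a possible reading. It does not settle the matter, because it relies on the worsening being a separate dated record, which nothing in the two documents requires. If every worsening always received its own post-dose onset, the protocol's second route would add little.

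A reader might infer several stronger things that the documents do not support.

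- *That such events are left out of every AE table.* The death table is not limited to treatment-emergent events, and the listings of SAEs and of AEs leading to discontinuation carry no explicit limit. Laboratory worsening is also shown through maximum post-baseline grades and shift tables (SAP 5.7.3.1).
- *That the SAP expressly excludes any AE known to start before first dose.* The clause that refers to this applies only to partial or missing dates, and its default is inclusion.
- *That AESI counts are heavily exposed.* Protocol 8.3.6 concerns newly identified malignancy and cases of active TB or ILD after the first administration, where worsening of an existing condition matters little. The wider categories in SAP Appendix 8, such as hypersensitivity and cardiovascular events, leave some room for it.

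**Conclusion.** The conflict is real. The protocol has a worsening route, the SAP does not, the affected summaries are restricted to treatment-emergent events, and Appendix 2 declares no change. The consequence is conditional: a screening-onset AE that worsens on study intervention *can* be omitted from the treatment-emergent AE and AESI summaries, and so from the secondary safety endpoint, if the worsening is kept on the pre-dose record and occurrence is read as onset. It is counted if entered as a new AE with a post-dose date.

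The number affected cannot be computed and may be small. It would be tempting to multiply assumed rates of screening AEs and of worsening into a count per arm, but the documents support no such rates, and an omitted event is not the same as an omitted participant. Nor can one say that the SAP definition as a whole can only lower the counts. That is true of dropping the worsening route, but the SAP's timing rule is not worded identically to the protocol's first route. The point is a modest one, worth correcting because it touches a stated endpoint and costs little to put right.

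**What to change.** In SAP 5.7.2, restore the protocol's second route. Suggested wording: an AE is treatment-emergent if it occurs at or after the first administration of study intervention, or if it reflects a preexisting condition, including an AE with onset in screening, that has worsened since baseline. Add that a post-dose worsening is analysed with the date of worsening as its start, whichever way the site entered it. Check the eCRF completion instructions, so that the date of worsening can be recovered from the data. If the sponsor prefers the timing rule alone, that choice should be declared and justified in SAP Appendix 2.

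The cost is two SAP sentences and possibly a few site queries on existing records. AE percentages may come out slightly higher.
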